2.1 Study Design

[figure not shown]
This is an observational, retrospective cohort study. Eligible patients will be identified from the Syapse Learning Health Network database and medical chart review will be conducted by Syapse Certified Tumor Registrars (CTRs). All study data are secondary data and will have been collected retrospectively from existing clinical data originally collected as part of routine care. This single-arm descriptive analysis will describe the patient characteristics, clinical attributes and treatment patterns of A/MBC patients with HR+/HER2- disease, who were treated with palbociclib + AI as first-line therapy. Additionally, clinical effectiveness outcomes for these patients will be evaluated between Feb 2015 and July 2019.

Study population

The study will include adult patients 18 years or older, diagnosed with HR+/HER2- A/MBC who initiated palbociclib combination therapy with AI as the first-line therapy on or after 03 February 2015 up to and including 31 July 2019. Patients for this study will be identified from the Syapse Learning Health Network database.

Preliminary analysis identified up to 1,074 patients with evidence of key primary inclusion criteria: breast cancer diagnosis and palbociclib treatment. Three to four hundred patients are expected to fulfil complete study inclusion criteria. Given the inclusion criterion requiring a qualifying treatment identification period between 03 February 2015 through 31 July 2019, and assuming a data cutoff date of 01 February 2020, the minimum follow-up available is therefore 6 months.

PFIZER CONFIDENTIAL

Data source

Patients will be identified and data will come from the Syapse Learning Health Network database which includes both inpatient and outpatient clinical and molecular data captured through manual abstraction and interoperative data feeds from a number of health system source systems, including:

- *Electronic medical record (EMR), including inpatient, outpatient oncology, ambulatory, surgical, etc.*
- *Electronic data warehouse (EDW)*
- *Laboratory information system (LIS)*
- *Picture archiving and communication system (PACS)*
- *Hospital based cancer registries*
- *Computerized physician order entry (CPOE)*

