2.2 Study Objectives

Primary Objectives:

- 1) *Among patients with HR+/HER2- A/MBC receiving palbociclib combination therapy with AI as first-line therapy:*
 - a. *Describe demographic and clinical characteristics.*
 - *Demographic characteristics will include age, sex, race, insurance status, menopausal status, and region of residence at A/MBC diagnosis.*

[figure not shown]
PFIZER CONFIDENTIAL

- *Clinical characteristics will include variables such as, stage of initial diagnosis, histology, Eastern Cooperative Oncology Group (ECOG) performance status (where ECOG score unavailable, Karnofsky performance status will be converted to corresponding ECOG score) and comorbid disease burden utilizing the Charlson Comorbidity Index, HER2 and estrogen receptor (ER)/ progesterone receptor (PR) status, BRCA status, number and sites of distant metastasis at A/MBC diagnosis (visceral (defined as liver, lung, peritoneum, and pleural nodules), non-visceral, bone only); modalities of treatment received prior to A/MBC diagnosis (chemotherapy, hormone therapy, surgery, radiation therapy) documentation of endocrine sensitivity and endocrine resistance if hormone therapy was received in the adjuvant setting, time to metastasis (time between initial and metastatic diagnosis) and disease free interval (time between completion of adjuvant therapy and diagnosis of A/MBC).*
- b. *Describe treatment patterns.*
 - *Distribution of regimens from the diagnosis of A/MBC through the end of the record.*
 - *Sequence of regimens across lines, through the end of the record of systemic therapy.*
 - *Description of the dosing will include the starting dose, end dose, dose adjustment (dose increase and dose reduction), type of dose adjustment (dose modification, schedule changes, dose delay, or hold) discontinuation, reason (including progression, end of planned therapy, insurance changes, schedule change, dose delay, hold, cost, patient refusal, toxicity), and time to dose adjustment (discontinuation).*
- 2) *Among patients receiving palbociclib + AI as first-line therapy, examine clinical effectiveness outcomes including:*
 - a. *Real-world progression-free survival (rwPFS) will be assessed for the first-line therapy.*
 - b. *Real-world overall survival (rwOS) will be assessed from the start of the first-line therapy.*
 - c. *Real-world time to next therapy (rwTTNT) will be assessed from the start of the first-line therapy.*

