5 ENDPOINTS AND COVARIATES

Primary Endpoints-

1. To summarize the demographic and clinical characteristics.
Demographic characteristics will include

PFIZER CONFIDENTIAL

- Year of initial, metastatic and AMBC diagnoses;
- age at initial diagnosis, A/MBC diagnosis, start of palbociclib treatment and death;
- sex;
- race;
- ethnicity
- insurance status;
- menopausal status;
- region of residence at A/MBC diagnosis.

Clinical characteristics will include

[figure not shown]
- stage of initial diagnosis;
- histology;
- Eastern Cooperative Oncology Group (ECOG) performance status (where ECOG score unavailable, Karnofsky performance status will be converted to corresponding ECOG score);
- prior surgery (and type);
- prior radiation therapy (and type);
- comorbid disease burden (see Section 9.2);
- Charlson comorbidity index
- Sites of metastasis – visceral (liver, lung, peritoneum and pleural nodules), non-visceral, bone only
- Number of metastatic sites
 - Number of lesions in the site
 - Disease burden in the liver, lungs, bone
- time to metastasis (time between initial and metastatic diagnoses)
- HER2 and estrogen receptor (ER)/ progesterone receptor (PR) status;
- BRCA status
- modalities of treatment received prior to A/MBC diagnosis (chemotherapy, hormone therapy, surgery, radiation therapy);
 - Documentation of endocrine sensitivity and endocrine resistance if hormone therapy received in adjuvant setting
- disease free interval (time between completion of adjuvant therapy and diagnosis of A/MBC).

2. To summarize treatment patterns.

Treatment patterns will be evaluated by the review of

- the distribution of regimens;
- sequence of regimens across the lines;
- description of dosing which will include the starting dose, end dose, dose adjustment (dose increase and dose reduction), type of dose adjustment (dose modification, schedule changes, dose delay or hold), discontinuation reason (including death, progression, end of planned therapy, insurance changes, schedule change, dose delay, hold, cost, patient refusal, toxicity), and time to dose adjustment

PFIZER CONFIDENTIAL

[figure not shown]

3. To summarize the effectiveness outcomes of treatment-
 - a. Real-world progression-free survival (rwPFS) for the first-line therapy at time points 3, 6, 12, 18, 24, 30, and 36 months;
 - b. Real-world overall survival (rwOS) from the start of the first-line therapy at time points 6, 12, 18, 24, 30, and 36 months.

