8.2.3 Medication/ Treatment Data

Treatment Patterns

PFIZER CONFIDENTIAL

[figure not shown]

Table 15.4.1. Total Number of Lines Per Patient from the Diagnosis of A/MBC

Variable, n (%)	palbociclib + AI (n=xxx)
1	n (x.x%)
2	n (x.x%)
3	n (x.x%)
4	n (x.x%)
≥5	n (x.x%)

Table 205.4.2. Treatments by Line of Therapy from the Diagnosis of A/MBC

Line	Regimen (Agents)	palbociclib + AI (n=xxxx)
1 (N=xxx)	XXXXXX	n (x.x%)
	XXXXXX	n (x.x%)
	XXXXXX	n (x.x%)
	...	
2 (N=xxx)	XXXXXX	n (x.x%)
	XXXXXX	n (x.x%)
	XXXXXX	n (x.x%)
	...	
3 (N=xxx)	XXXXXX	n (x.x%)
	XXXXXX	n (x.x%)
	XXXXXX	n (x.x%)
	...	
	XXXXXX	n (x.x%)
4 (N=xxx)	XXXXXX	n (x.x%)
	XXXXXX	n (x.x%)
	XXXXXX	n (x.x%)
	...	
5 (N=xxx)	XXXXXX	n (x.x%)
	XXXXXX	n (x.x%)
	XXXXXX	n (x.x%)
	...	

Figure 215.4.3. Proportion of Patients with Regimen by Line of Therapy from the Diagnosis of A/MBC

PFIZER CONFIDENTIAL

Dosing Description

Table 15.4.4. Dosing at Start and End of Treatment, n (%)

Starting dose	End dose				
	75mg	100mg	125mg	Unknown	Total
75 mg	n (x.x%)				
100 mg	n (x.x%)				
125 mg	n (x.x%)				
Unknown	n (x.x%)				
Total	n (x.x%)				

Table 15.4.5. Dosing description

Variable/Statistic	palbociclib + AI (n=xxx)
Dose adjustment	
No adjustment	n (x.x%)
Increase	n (x.x%)
Decrease	n (x.x%)
Unknown	n (x.x%)
Type of dose adjustment	
Hold	n (x.x%)
Schedule change	n (x.x%)
Dose delay	n (x.x%)
Hold	n (x.x%)
Cost	n (x.x%)
Patient refusal	n (x.x%)
Toxicity	n (x.x%)
Time (days) to Dose Adjustment	
n	xx
Mean (SD)	x.x (x.xx)
Median (Q1, Q3)	x.x (x.x, x.x)
Min, Max	x.x, x.x
Discontinuation	
No	n (x.x%)
Yes	n (x.x%)
Discontinuation reason	
Progression	n (x.x%)
Intolerance/Toxicity	n (x.x%)
Other/Unknown	n (x.x%)
Patient choice	n (x.x%)
Treatment for other diseases	n (x.x%)
Left health system	n (x.x%)
End of planned therapy	n (x.x%)
Changes in insurance	n (x.x%)
Death	n (x.x%)
Hospice referral	n (x.x%)

PFIZER CONFIDENTIAL

[figure not shown]
Table 15.4.5. Dosing description

Variable/Statistic	palbociclib + AI (n=xxx)
Physician choice	n (x.x%)
Treatment ongoing	n (x.x%)

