Therapy start date	Year, month, day
Therapy end date	Year, month, day
Start reason	Recurrence; Progression; Other reason not related to worsening disease
Start reason source date	Year, month, day (can be linked to clinician confirmation date of recurrence/progression if start reason is recurrence/progression)
Stop reason	Categories including: Progression; Toxicity; End of planned therapy; Insurance changes; Treatment ongoing; Other
Stop reason source date	Year, month, day (can be linked to clinician confirmation date of recurrence/progression if stop reason is recurrence/progression)
Treatment part of clinical trial	Yes; No
Palbociclib-specific variables (captured in addition to above variables)	
Combination AI partner	Letrozole, Anastrozole, Exemestane
Concomitant LHRH Agonists	Goserelin (Zoladex), Histrelin (Vantas), Leuprolide (Eligard, Lupron), Triptorelin (Trelstar)
Dose 1 (start dose)	125mg, 100mg, 75mg
Dose 1 start date	Year, month, day
Dose n (where n>=2)	125mg, 100mg, 75mg
Dose n start date	Year, month, day
Dose n adjustment type or reason	Categories include schedule change; dose delay; hold; cost; patient refusal; toxicity

Variables that will be derived from curated data will include the following:

Data Elements	Description
-----------------------------	---------------------------

PFIZER CONFIDENTIAL

Age at A/MBC diagnosis	Age in years; age categories: <50, 50-64, 65 –74, ≥75 years (Exact list will depend on the expert de-ID approach)
Age at start of palbociclib treatment	Age in years; age categories: <50, 50-64, 65 –74, ≥75 years
Date of death	If patient vital status = deceased, date of death from the medical record (capturing from EMR, registries, third party integrations) (Availability of the exact date will depend on the Expert de-ID approach)
Palbo dose change ever	Yes; No
Disease Free Interval (DFI)	Months from the end of adjuvant therapy to the date of disease recurrence ≤12 months, 13-24 months, 25-36 months >36 months Unknown
Endocrine sensitivity	≥12 months without recurrence/progression after completion of endocrine therapy in the adjuvant setting

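### Table 15.4.5 lists reasons as types of dose adjustment and has no dose-modification row, so it cannot give the type distribution that objective 1b asks for

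*SAP*

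**What the plan says.** Objective 1b in SAP section 2.2 asks for "type of dose adjustment (dose modification, schedule changes, dose delay, or hold". Section 5 uses the same four categories, "type of dose adjustment (dose modification, schedule changes, dose delay or hold", and section 7.2 repeats them for the analysis.

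Section 8.2.3 holds the shell that reports this variable, Table 15.4.5. Under "Type of dose adjustment" it has seven rows: Hold, Schedule change, Dose delay, Hold again, Cost, "Patient refusal" and Toxicity.

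Appendix 2 (section 9.2) defines the source as a single element, "Dose n adjustment type or reason", described as "Categories include schedule change; dose delay; hold; cost; patient refusal; toxicity". The mg level at each later dosing step is a separate element, "Dose n (where n>=2".

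**The concern.** Type and reason are two attributes of the same event: a hold because of toxicity has one of each. The planned text treats type as a variable with four values. The shell uses that heading for a list that is part type and part reason and omits one of the four values.

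At stake is a variable named in a primary objective. A reader of the finished table could not tell how adjustments divide among the four types. Nor could they tell how many adjustments of any kind were made for toxicity, because a toxicity-driven hold could sit under either label.

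**Working it through.** There is no sample size, power or event figure to reproduce. The study is descriptive ("This single-arm descriptive analysis will describe the patient characteristics, clinical attributes and treatment patterns"), so the check is a comparison of labels.

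| Label | Sections 2.2, 5, 7.2 | Appendix 2 field | Table 15.4.5 type block |
|---|---|---|---|
| Dose modification | type | not listed | no row |
| Schedule change | type | listed | one row |
| Dose delay | type | listed | one row |
| Hold | type | listed once | two rows |
| Cost | not a type | listed | one row |
| Patient refusal | not a type | listed | one row |
| Toxicity | not a type | listed | one row |

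**Counts.** Planned types: 4. Types with a row: 3. Missing: 4 − 3 = 1 (dose modification). Rows in the block: 3 distinct types + 1 duplicate + 3 reasons = 7. Distinct labels: 7 − 1 = 6, the same six as in the Appendix 2 field. That match accounts for the reason rows and for the missing dose-modification row. It does not account for the second Hold, because the field lists Hold once; that is a separate shell error.

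**Consequence if one code is recorded per adjustment.** Let r be the share of adjustments coded by a reason. The type rows together then cover 1 − r of adjustments. The SAP gives no value for r, so these are assumed:
- r = 0.1: 1 − 0.1 = 90% covered
- r = 0.3: 1 − 0.3 = 70% covered
- r = 0.5: 1 − 0.5 = 50% covered

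The block does not show the type of the remaining adjustments, and it does not show the reason for those coded by type.

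**Consequence if several codes are allowed.** A toxicity-driven hold can appear under both labels. Nothing is lost where both were recorded, but the rows overlap and no longer form a distribution of types.

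**Missing data.** Section 6 says absent data are reported as not documented, and section 7.1 says percentages always include the missing category. The type block has no such row, so an adjustment with only a reason recorded has nowhere to show that its type is unknown.

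**Neighbouring lists.** The discontinuation-reason text in sections 2.2, 5 and 7.2 includes schedule change, dose delay and hold. These are adjustment types in the same sentence, and none of them is a row in the discontinuation-reason block of Table 15.4.5.

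**The case against.** The strongest reply is that this is an untidy shell in a descriptive study without hypotheses, and that most of the information is available elsewhere. Much of that stands.

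- A reader might infer that mg changes go unreported. They do not. The block above in the same table has Increase and Decrease rows, Table 15.4.4 crosses starting dose with end dose, and section 5.1 defines the number of reductions and increases. These do not replace the type block, however. A hold, delay or schedule change at unchanged mg is neither an increase nor a decrease, and none of these displays links a change to its reason.
- A reader might infer that every row is an undercount. That needs one code per adjustment. Appendix 2 does not say the field is single-select, and its wording leaves open that the category list is incomplete.
- A reader might infer that the counting unit is undefined. Section 7.1 makes patients the default for categorical variables, and the tables that count events (15.1.14, 15.1.15, 15.1.17 and 15.1.18) say so in a footnote. What remains open is whether a patient with several adjustments may appear in several rows.
- Cost, patient refusal and toxicity do belong to the dosing description, since the same sentences list them as reasons. The fault is that they stand under a type heading, not that they are reported.
- Splitting the Appendix 2 field itself could mean returning to charts. Section 1 shows that a manuscript draft already existed when this version was amended, so a remedy that needs new abstraction would be hard to justify.

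**Conclusion.** The contradiction is plain on the face of the SAP: three sections set four types, and the shell omits one, duplicates another and adds three reasons. Followed as written, Table 15.4.5 cannot deliver the type distribution of objective 1b.

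The direction of the distortion depends on a coding rule that the SAP does not state: undercounted type rows under single coding, overlapping rows under multiple coding. The size cannot be computed. The 90%, 70% and 50% coverage figures only illustrate assumed values of r under single coding. The documents do not support a claim that the reported figures will be wrong by any particular amount, and nothing here bears on the survival-type outcomes.

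The point is worth correcting because the variable is named in a primary objective and the repair is small.

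**What to change.** Replace the block in Table 15.4.5 with two.

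1. **Type:** dose modification, schedule change, dose delay, hold (once), not documented. Derive dose modification by comparing the mg level of Dose n with that of Dose n−1, whatever code was recorded.
2. **Reason:** toxicity, cost, patient refusal, other, not documented.

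State under the table that patients are counted and whether a patient may appear in more than one row. Put an attribute that was not coded in its not-documented row, as sections 6 and 7.1 require.

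At the same time, reconcile the discontinuation-reason lists in sections 2.2, 5 and 7.2, which include schedule change, dose delay and hold, with the discontinuation rows of the same table.

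The cost is a revised shell and a short derivation from fields already abstracted; no new chart abstraction is required. The downside is a visible not-documented share wherever only one attribute was coded, which reports honestly what the field can support.

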of the 2nd line for patients with >1 line of therapy, date of last contact, or end of study period.

- Real world time to treatment discontinuation (rwTTD)- It is defined as length of time from the start of palbociclib + AI treatment to the earliest of the following: date the patient discontinues first-line treatment, date of death, last known usage of first-line treatment, or end of study period.
- Real world time to next treatment (rwTTNT)- It is defined as length of time from the start of palbociclib + AI treatment to the earliest of the following: subsequent line of therapy initiation, date of death, date of last contact, or end of the study period.
- Real world time to chemotherapy (rwTTC)- It is defined as length of time from the start of palbociclib + AI treatment to the earliest of the following: the day before the start of subsequent chemotherapy for patients with evidence of chemotherapy, or date of death for any reason. Or, where censored, the latest of date of last contact, or end of the study period.
- Real world time to dose adjustment (rwTTDA)- It is defined as length of time from the start of palbociclib + AI treatment to the earliest of the following: date of first-line treatment dose adjustment, date of death, date of first-line treatment discontinuation, date of last contact or end of study period.

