Kaplan-Meier survival analysis is used to descriptively characterize time to event outcomes. In this study, following time to event outcomes will be analyzed-

- Time to Real-world overall survival (rwOS)

[figure not shown]
The time origin for analysis of rwOS is start of the first-line therapy, and the terminal event is death. For patients not known to be deceased at the time of analysis, rwOS will be censored at the earliest of the last date of last contact or the end of the study period.

- Time to Real-world progression-free survival (rwPFS)

The time origin for analysis of rwPFS is start of the first-line therapy. Patients without a clinician-assessed progression event or death will be censored at the earliest of the following events: date of initiation of the 2nd line for patients with >1 line of therapy, date of last contact, or end of study period.

- Real world time to treatment discontinuation (rwTTD)

PFIZER CONFIDENTIAL

The time origin for analysis of rwTTD is start of the first-line therapy. Patients without first-line treatment discontinuation and who did not die will be censored at the earliest of the following events: last known usage of first-line treatment, or end of study period.

- Real world time to next treatment (rwTTNT)

The time origin for analysis of rwTTNT is start of the first-line therapy. Patients without a subsequent line of therapy initiation and who did not die will be censored at the earliest of the following events: date of last contact, or end of the study period.

- Real world time to chemotherapy (rwTTC)

The time origin for analysis of rwTTC is start of the first-line therapy. Patients who did not receive subsequent chemotherapy and who did not die will be censored at the latest of the following events: date of last contact, or end of the study period.

- Real world time to dose adjustment (rwTTDA)

The time origin for analysis of rwTTDA is start of the first-line therapy. Patients without a first-line treatment dose adjustment will be censored at the earliest of the following events: first-line treatment discontinuation, date of death, date of last contact, or end of the study period.

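### A stop recorded because the patient left the health system counts, as the SAP is written, as an rwTTD event rather than as censoring

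*SAP*

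**What the plan says.** **rwTTD.** Section 5.1 runs the time from the start of palbociclib + AI to the earliest of "date the patient discontinues first-line treatment, date of death, last known usage of first-line treatment, or end of study period". Section 7.2 separates events from censoring: "Patients without first-line treatment discontinuation and who did not die will be censored at the earliest of the following events". The two dates it then offers are the last recorded use of the first-line regimen and the close of the study. Neither section refers to the reason for a stop.

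**Reasons for stopping.** Table 15.4.5 has a No/Yes item for discontinuation, followed by a block of discontinuation reasons. One row of that block is "Left health system" and the last is "Treatment ongoing". In Appendix 2 (section 9.2) the abstracted stop-reason field is described as "Categories including: Progression; Toxicity; End of planned therapy; Insurance changes; Treatment ongoing; Other".

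**Holds, delays and schedule changes.** Section 5 gives "discontinuation reason (including death, progression, end of planned therapy, insurance changes, schedule change, dose delay, hold, cost, patient refusal, toxicity", and section 7.2 repeats the list. The same sentences also name schedule changes, dose delay and hold as types of dose adjustment. Table 15.4.5 shows these items only under type of dose adjustment. Appendix 2 puts them only in the dose-adjustment field: "Categories include schedule change; dose delay; hold; cost; patient refusal; toxicity".

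**rwTTDA.** In section 7.2 a first-line dose adjustment is the event, and first-line discontinuation is one of the censoring dates.

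**The concern.** Leaving the health system ends observation. It does not show that treatment ended. The SAP already has the right date for such a patient, last known usage of first-line treatment, but the section 7.2 rule opens that date only to patients without a discontinuation. A patient tabulated as discontinued for leaving the system is therefore an event under the written rule. Each such event pulls the Kaplan-Meier curve down, and it enters the rwTTD median, the landmark estimates from 3 to 36 months and the rwTTD Cox model.

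The second matter is the disagreement between the reason lists. A programmer who follows sections 5 and 7.2 could treat a hold as a discontinuation reason. One who follows Table 15.4.5 and Appendix 2 would treat it as a dose adjustment. On the first reading the same record could be an rwTTD event and either the rwTTDA event or its censoring date. On the second it is an rwTTDA event only.

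**Working it through.** The SAP states no rwTTD median, no departure rate and no sample-size calculation, so there is no figure of its own to reproduce. The check has two parts.

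**1. Following one record through the text**

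- A patient has a first-line stop recorded with the reason of leaving the health system. In Table 15.4.5 this patient is Yes for discontinuation and is counted in that reason row.
- Section 7.2 asks whether the patient is without first-line discontinuation. The answer is no, so the censoring rule does not apply.
- Section 5.1 then takes the discontinuation date as the end of rwTTD. Result: an event.
- A patient who leaves with no stop recorded is already censored at last known usage. The problem is confined to departures that were coded as stops.

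**2. Size, on assumed inputs**

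Let h be the monthly hazard of true discontinuation or death and l the monthly hazard of a departure recorded as a stop, both constant and independent.

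- True median = ln 2 / h.
- Median when departures count as events = ln 2 / (h + l).
- Share of counted events that are departures: q = l / (h + l).
- Hence the observed median = (1 − q) × the true median.

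A simulation of 200,000 patients used exponential times and administrative censoring uniform from 6.08 to 60 months. The lower limit is 31 July 2019 to 1 February 2020: 185 days / 30.4375 = 6.08. It gave:

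| True median (months) | q = 2% | q = 5% | q = 10% |
|---|---|---|---|
| 12 | 11.8 | 11.4 | 10.9 |
| 18 | 17.6 | 17.0 | 16.2 |
| 24 | 23.6 | 22.8 | 21.6 |

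These agree with (1 − q) × median to within 0.1 month (18 × 0.98 = 17.6; 18 × 0.95 = 17.1; 18 × 0.90 = 16.2). Censoring the departures instead returned 12.0 to 12.1, 18.0 and 24.0 to 24.1.

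The same formula can start from an annual rate of recorded departures, with l = −ln(1 − rate)/12. For a true median of 20 months, h = 0.6931/20 = 0.03466:

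| Annual rate | l | Observed median = 0.6931/(h + l) | Implied q |
|---|---|---|---|
| 3% | 0.00254 | 18.6 | 7% |
| 5% | 0.00427 | 17.8 | 11% |
| 10% | 0.00878 | 16.0 | 20% |

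For a true median of 24 months the observed medians are 22.1, 20.9 and 18.4, with q about 8, 13 and 23%. The higher annual rates thus assume that a fifth or more of all counted events are departures, so the range q = 2 to 10% is the more restrained illustration.

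No effect of holds or delays can be computed. The SAP gives neither their frequency nor a rule by which one would end first-line treatment.

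**The case against.** The strongest reply is that Table 15.4.5 is a descriptive dosing table and is not stated to feed rwTTD. The rwTTD tables are titled as using regimen-based lines of therapy, and line end dates are derived variables in Appendix 2. No sentence ties a stop reason to event status. The study is single-arm and descriptive, with section 3 marked not applicable, so no decision rule turns on the result. All of this is fair, and it limits the weight of the point. It does not remove it: the only written rule for separating rwTTD events from censoring is the presence or absence of a discontinuation, and the SAP's own tabulation classes a departure as one.

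A reader might infer more from the same text in two places, and the document does not support either inference.

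- *Patients with ongoing treatment become events.* That row is most naturally the code for no stop. The table has its own No/Yes item, and section 7.2 censors patients without a discontinuation. The table of age at death likewise carries a row for patients who are alive. The row is a table-shell matter only.
- *Holds and delays shorten rwTTD.* They are not in Table 15.4.5's list of discontinuation reasons or among the named stop-reason categories, and nothing says that a hold ends first-line treatment. Section 2.2 punctuates the sentence differently and can be read as one pooled reason list for adjustments and discontinuations. What stands is that the lists in sections 5 and 7.2 disagree with Table 15.4.5 and Appendix 2.

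For rwTTDA, a departure recorded as a discontinuation is censored, which is appropriate. The departure problem belongs to rwTTD alone.

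**Conclusion.** The point holds for departures from the health system. The rule as written turns a recorded departure into an rwTTD event and biases rwTTD downward. The relative shift in the median is about the share of counted events that are departures: 0.2 to 2.4 months for true medians of 12 to 24 months and shares of 2 to 10%. The medians, the shares and the constant, independent hazards are assumptions; the SAP supplies none of them. If few departures are coded as stops, the effect is small. Censoring removes the bias provided that leaving the system is unrelated to the patient's prospect of stopping treatment.

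The conflict between the lists is a real inconsistency affecting how rwTTD and rwTTDA are kept apart, but its numerical effect is unknown. Because both are listed primary endpoints and two careful programmers could code them differently from this text, the wording should be corrected.

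**What to change.** 1. In sections 5.1 and 7.2, state that a stop recorded for leaving the health system is not an rwTTD event and is censored at last known first-line usage.
2. Reconcile the reason lists in sections 5 and 7.2 (and the parallel sentence in section 2.2) with Table 15.4.5 and Appendix 2. Schedule change, dose delay and hold should have one stated role in the endpoint definitions, so that a single record cannot be an rwTTDA event and also an rwTTD event or an rwTTDA censoring date.
3. As a tidy-up of the shell, label the ongoing-treatment row as not discontinued, or move it out of the reason block.

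The cost is a few sentences in the SAP and about one line of programming. Stop reason is already abstracted, and Table 15.4.5 already requires departures to be identified, so no new data are needed.
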